Sample Size and Power analysis: Based on our previous study of nurse coaching using MI to improve disease self-management (23), we found improvement in self-efficacy scores significantly higher in the intervention group compared to the control group. Based on these data, we expect to find self-efficacy scores to be 4.03 and 3.64, for the intervention and control group respectively, with a standard deviation of 0.70. Table 1 presents the sample size calculations for the number of eligible patients needed to detect significant differences in self-efficacy scores between the cohorts.

According to the anticipated enrollment calculations above, we expect to enroll at least 150 patients in each of the intervention and control cohorts. This sample size will be sufficient to detect differences between the two groups as demonstrated in Table 1. In the previous study, we had a low overall attrition rate of 16% using a similar intervention design with comparable demand on participants for time and response. Even under the conservative assumption that design effects and dropout rates may result in a reduced sample size of 100 per treatment group, our study will still have at

Patient and Provider Engagement and Empowerment through Technology $(P^2E^2T^2)$ to Improve Health in Diabetes

least 80% power to detect the specified clinically important effect size. We will not enroll more than 350 participants in total.

Difference in Self- Efficacy Scores	Significance Level (Alpha)	Power (1-Beta)	Intervention, N	Control, N
0.20	0.05	0.80	219	219
0.25	0.05	0.80	134	134
0.30	0.05	0.80	92	92
0.35	0.05	0.80	67	67
0.40	0.05	0.80	51	51

8) Recruitment Methods

We propose several approaches to accomplish our recruitment goals within the time frame of the funded study. These will be used in concert with one another to achieve the full sample.

Potential study participants will be identified by a query of the Electronic Health Record (EHR) at UC Davis Health System for specific elements essential for eligibility (over age 18; assignment to one of the participating primary care clinics & providers; diagnosis of Diabetes Mellitus-Type 2; and HgbA1C value of over 6.5 %). Affiliated clinic providers will be notified in advance that eligible patients from their census will be contacted for study participation.

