9) Compensation to the Subjects

All subjects, regardless of treatment arm, will be given a health monitoring device at the end of the study. Upon completion of study questionnaire and their regularly scheduled visit with their primary care physician all participants will receive \$50 at baseline, 3 and 9 months. Those participants in the intervention $(P^2E^2T^2)$ arm will receive a health monitoring device at the beginning of the study; and those participants in the Care Coordination arm of the study will also receive a health monitoring device upon successful completion of all study questionnaires. If participants do not complete all aspects of the study, they will not receive the health monitoring sensor device. Each sensor device is worth approximately \$75.

10) Study Timelines

Each individual will be enrolled in the study for 9 months. Each participant will complete a study questionnaire at baseline, 3 months and 9 months. Estimated duration of the study completion is 24 months from start of enrollment (January 1^{st} , 2016 – December 31^{st} , 2017).

11) Study Endpoints

Outcomes to be evaluated include: i) Quality of Life (QOL) measures; ii) Self-efficacy; iii) Readiness to Change; and iv) Clinically Relevant Indicators (HgbA1C, HDL, LDL, triglycerides). All measures will be collected in both groups at the study timelines. At baseline (time of recruitment), all participants will be asked to complete the surveys and the care coordinator will request the primary care provider orders for the laboratory tests measuring the clinical indicators. The lab tests are routinely used to monitor diabetes management and are typically covered by insurance. Should the patient not have a payment source for the laboratory assays, the project will cover the cost of the laboratory tests. At 3 months and 9 months, surveys links will be sent by email to each participant along with a reminder to complete the laboratory work ordered by their provider. If not completed, reminder emails or phone calls may be made by the study team. The primary endpoints of the study are: baseline data; data at the completion of five sessions of support calls during the 3 months of the intervention; and data at 6 months after the end of the intervention (9 months after baseline).

12) **Procedures Involved**

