Historical data, such as completed lab work values as identified above (Study Endpoints section), will be gathered by querying the EHR for all participants involved in the study. This will be accomplished by working with the Health Informatics for research group, led by [name].

All data and data identifiers related to this study will be destroyed seven years after completion of the study. All data findings from the study will be presented as aggregate data with no individual subject identifiers.

Subjects will be using commercial off-the-shelf (COTS) sensors, smart phone applications, and web-based physical activity dashboard technologies. Participants must agree to use the sensors and applications required for data collection. If they are unwilling to use this sensor, they will not be able to participate. Immediately following consent and randomization into the "Care Coordination" and "P²E²T²" arms, project staff will assist participants with technology set-up, configuration, use, and ensure that subjects understand the commercial terms of service agreements, before they begin the trial. In order to further protect individual privacy, subjects in the P²E²T² arm may choose to share with their coach only portions of the data streams from their devices/apps. That is, subjects have the option to filter the data streams shared with their coach by time of day, and specific metric (i.e. steps counted, calories burned, etc.).

Variable	Measure	Data Collection		
v ar lable	Measure	Baseline	3 months	9 Months
Age, Gender,	Demographic Data Form	Х		
Race/Ethnicity, Education				
Level, Income Level and				
Insurance Type				
Specific Aim 1				
Focus Groups		Х	Х	Х
Specific Aim 2				
Self-Efficacy	Diabetes Empowerment Scale –	Х	X	Х
	Short Form (DES-SF)			
Readiness to Change	Readiness to Change Survey	Х	Х	Х
Clinical Indicators	Electronic health record	Х	Х	Х
(Abstracted)				
	Patient Health Questionnaire	Х	Х	Х
	depression scale-9 (PHQ-9)			
Quality of Life	Perceived Stress Scale (PSS)	Х	X	Х
Quality of Life	PROMIS Measures – Physical	Х	X	Х
	Function SF, Emotional Distress			
	SF, Sleep Disturbance			

15) Provisions to Monitor the Data to Ensure the Safety of Subjects

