Patient and Provider Engagement and Empowerment Through Technology Program to Improve Health in Diabetes

PI: [name]

January 11, 2019

NCT number: NCT02672176

Analytical and Statistical approaches

We will use Stata v15.0 (Stata Corp, College Stations Tx 2017) for all statistical analyses. Descriptive analysis will yield means/standard deviations for continuous variables and frequencies for categorical variables. We will examine distributions to determine whether data meets assumptions for planned statistical analyses. We will compare patient demographic and health-related characteristics between the individuals in the intervention group and the usual care group. We will compare continuous variables using a Student's t test or the Wilcoxon Signed-Rank test, and will compare categorical variables using the chi-squared test and Fisher's exact test, as appropriate. We will compare number of steps per week at baseline (Week 2) versus 3 months (Week 13), baseline versus 9 months (Week 37) and 3 months versus 9 months, using a paired t-test to evaluate the change in physical activity over time.

We will calculate change in outcomes over time as the difference between baseline and 3 months, and baseline and 9 months for diabetes self-efficacy scores, depression severity (PHQ-9), patient stress score, and PROMIS measures (Emotional distress anxiety, and physical functioning). We will use Student's t test to compare the change in outcome between usual care and intervention groups (Significance level: $p \le .05$).

In the primary analysis, we will estimate the difference over time in the effects of the intervention over usual care in the study participants. This is an intent to treat analysis, with the assumption that any dropouts are missing at random. We will also use an analytical method (Mixed model) which accounts for the missing data contributed by participants who dropped out from the study. Lastly, we will conduct a sensitivity analysis to determine whether there is a difference with regards to the significance of our findings when we exclude participants who drop out from the analysis. All participants, regardless of intervention completion, will be included in the intent to treat analysis.

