We will use multivariate regression modeling for all hypotheses testing to estimate withingroups and across group effects of the intervention on the outcome (significance level: $p \le$ 0.05). The mixed effects models will evaluate the impact of the intervention over time in the outcomes of Diabetes Self-Efficacy, depressive symptoms, and Perceived Stress Score (PSS). We will include a binary indicator for intervention group assignment, and a group- by-time interaction term in the models to compare improvement over time between the intervention group and usual care group. We will assess all variables for collinearity before including in the model. We will evaluate model fit using deviance tests for nested models, the Akaike Information Criterion, and the Bayesian Information Criterion for non-nested models. We will assess the estimates for the fixed effects using a pre-determined significance level (p < 0.05) on two sided tests and 95% confidence intervals. We will use the same approach for analyzing primary and secondary outcomes analyzing the effect of the intervention at baseline, 3 and 9 months.

We will conduct a post-hoc analysis examining the relationship between stage of change at baseline and intervention outcomes. We hypothesize that there might be differences in who the intervention benefits most – and will explores whether readiness to change status might be a tool for screening potential participants for inclusion in future trials or interventions.

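### The protocol's primary endpoints are visit times, baseline included; no outcome variable is designated primary, and several are tested at 0.05 without error control

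*Protocol*

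**What the plan says.** **Protocol section 11 (Study Endpoints)** opens with an unranked list: "Outcomes to be evaluated include: i) Quality of Life (QOL) measures; ii) Self-efficacy; iii) Readiness to Change", followed by four laboratory indicators (HgbA1C, HDL, LDL, triglycerides). It then says: "The primary endpoints of the study are: baseline data; data at the completion of five sessions of support calls" and closes the list with data six months after the intervention ends, that is, 9 months from baseline. The sentence names three times and no variable.

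**Protocol section 7 (Number of Subjects)** bases the calculation on one variable. Table 1 gives the numbers "needed to detect significant differences in self-efficacy scores between the cohorts", with expected means of 4.03 and 3.64 and a standard deviation of 0.70. It does not call this outcome primary or say at which visit the difference is expected. The data collection table in section 14 measures self-efficacy with the short form of the "Diabetes Empowerment Scale" (DES-SF).

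**The SAP** names five outcomes for between-group t tests of change, each at 3 and at 9 months: self-efficacy, PHQ-9, stress, PROMIS anxiety and PROMIS physical function. It names three for the mixed models: self-efficacy, depressive symptoms and perceived stress. The threshold is 0.05 throughout. It also says: "We will use the same approach for analyzing primary and secondary outcomes", without listing either set, and in the same sentence includes baseline among the times at which the intervention's effect is analysed. Neither document mentions a multiplicity adjustment.

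**The concern.** A primary endpoint has to be a variable compared between arms at a stated time. Section 11 supplies only the times, and one of them precedes treatment. The plan therefore has no defined test of success.

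The hypothesis in protocol section 4 is broad: more engagement and better health outcomes than usual care. If self-efficacy showed no difference but another scale reached p<0.05, nothing written would prevent that scale from being presented as support for the hypothesis. The nominal 5% error rate would then not describe the trial's main claim.

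The order of dates adds to this. The SAP is dated January 11, 2019, and protocol section 10 estimates completion on December 31, 2017. A ranking of outcomes written in 2019 or later needs a basis that predates the data.

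**Working it through.** **1. The plan's own figure.** The plan gives no overall error rate. Its nearest figure is at least 80% power with 100 per arm, for self-efficacy.

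- Inputs (section 7): difference 4.03 − 3.64 = 0.39; SD 0.70; two-sided 0.05.
- Standard error = 0.70 × √(2/100) = 0.0990; 0.39/0.0990 = 3.94.
- Power = Φ(3.94 − 1.96) = 97.6%, so the statement holds.
- Table 1 itself does not reproduce. n = 2(0.70/d)²(1.960 + 0.842)² gives 193, 124, 86, 63 and 49 per arm, against 219, 134, 92, 67 and 51 printed. The printed numbers are larger, so the discrepancy is conservative. It is a separate matter and does not bear on this point.

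**2. Counting outcomes.**

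- Named in the SAP for change tests: 5. Named for the mixed models: 3, all among those five.
- Measured under protocol sections 11 and 14: DES-SF (1), readiness (1), laboratory indicators (4), PHQ-9, PSS and three PROMIS forms (5). 1 + 1 + 4 + 5 = 11.
- The six that are measured but have no named between-group SAP test are HgbA1C, HDL, LDL, triglycerides, sleep disturbance and readiness.

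**3. Chance of at least one p<0.05 with no true effect, one test per outcome, one visit.**

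- Independent outcomes, either direction: 1 − 0.95^k. For k = 5, 1 − 0.774 = 22.6%; for k = 11, 1 − 0.569 = 43.1%.
- Independent outcomes, favouring the intervention only (2.5% per test): 1 − 0.975^k. For k = 5, 11.9%; for k = 11, 24.3%.
- With a common correlation r, the test statistics are taken as normal with one shared component, outcomes scored so that higher is better, and the probability is integrated over that component.

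| Outcomes | Direction counted | r = 0 | r = 0.3 | r = 0.5 | r = 0.7 |
|---|---|---|---|---|---|
| 3 (mixed models) | either | 14% | 14% | 13% | 11% |
| 5 (change tests) | either | 23% | 21% | 18% | 15% |
| 5 (change tests) | favourable | 12% | 11% | 9% | 7% |
| 11 (all measured) | either | 43% | 37% | 30% | 22% |
| 11 (all measured) | favourable | 24% | 19% | 15% | 11% |

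The documents give no correlations; r from 0 to 0.7 is an assumption. The benchmark is 5% for the either-direction rows and 2.5% for the favourable rows.

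**4. Both visits counted.** With an assumed between-visit correlation of 0.5 and an outcome correlation of 0.5 to 0.3, the either-direction chance is 31–35% for five outcomes and 49–58% for eleven.

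**5. Naming the variable alone is not enough.** DES-SF tested at 0.05 at both 3 and 9 months has an error of 8.4% at a between-visit correlation of 0.7 and 9.5% at 0.3. One visit must decide, or alpha must be split.

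**6. Power after the change.** For the 0.39 difference at 100 per arm:

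- One visit at 0.05: 97.6%.
- Two visits at 0.025 each: Φ(3.94 − 2.24) = 95.5% per visit.

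**The case against.** The best defence is that self-efficacy is already the primary outcome in all but name. It is the only variable in the sample size, section 7 ties it to a clinically important effect size, and it comes first in both SAP lists. Much of this stands. A reader might infer that the powered outcome has no special standing at all; section 7 contradicts that. What is missing is the designation. Section 11, which should make it, puts times in its place, and the SAP gives self-efficacy the same threshold as depression and stress.

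A second objection concerns size. A reader might infer that the SAP tests eleven outcomes and that the false-positive rate is 43%. The SAP names five for between-group change tests. The other six could enter only through general wording about all hypothesis testing and about primary and secondary outcomes, and readiness otherwise appears only as a baseline stage in a post-hoc analysis. Eleven is thus an upper bound, and 43% also requires independence. Results favouring usual care could not support the hypothesis, so the favourable-direction figures, about half as large, are the closer measure of a false claim of benefit.

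Third, the dates might be read as showing that outcomes were ranked after the data were seen. The documents do not show this. December 2017 is an estimate, and neither document gives the actual last follow-up or database lock, or says when results were first examined.

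**Conclusion.** The point holds as a defect of designation. The sentence that should define the primary endpoint lists three times, one of them before treatment. No primary variable is named in either document, the SAP relies on a primary/secondary distinction it never makes, and nothing limits error across outcomes.

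At one visit with no true effect, the chance of at least one nominally significant outcome is about 15–23% for the five SAP-named outcomes, of which 7–12% is in the intervention's favour. If all eleven measured outcomes are tested, the upper bound is 22–43%, of which 11–24% is favourable. Counting both visits raises these figures. They rest on assumed common correlations from 0.7 to 0 and on one test per outcome. Even the three mixed-model outcomes at one visit give 11–14%, more than twice the nominal rate.

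**What to change.** **Protocol section 11 and the SAP.** Replace the primary-endpoint sentence. State that the single primary outcome is the DES-SF self-efficacy score, the variable the sample size is based on, and that baseline, 3 and 9 months are assessment times. Name one decisive between-group comparison: either one stated visit (3 or 9 months), or both visits with alpha split. Remove baseline from the SAP's list of times at which an intervention effect is analysed.

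**Secondary outcomes.** List every other outcome by name. Either apply a multiplicity adjustment such as Holm, or report estimates and confidence intervals with no confirmatory claim. Either choice is acceptable if stated.

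**Disclosure.** Give the date on which the designation was made, say that it rests on section 7 of the protocol, and state whether outcome data had been examined by then.

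**Cost.** Wording only. The primary comparison keeps about 98% power for the 0.39 difference at 100 per arm, or about 96% per visit if alpha is split. Secondary outcomes face a stricter threshold or carry no confirmatory claim. As an illustration, Holm's strictest step over ten secondaries is 0.05/10 = 0.005. An outcome with the same standardised effect (0.39/0.70 = 0.56) would have about 87% power there at 100 per arm; the documents give no expected effects for these outcomes.

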2. Orientation to the technology (in person meeting): A member of the research team will meet with each participant to orient them to both the wireless health and fitness tracking sensor, other health applications and the mHealth dashboard in UC Davis' Electronic Health Record, EPIC. The selected sensors and applications will track numbers of steps traveled, approximate calorie expenditure based on movement, sleep quality, heart rate, and components of logged nutrition data. The data wirelessly uploads to the participant's personal, or study supplied, Apple device (iPhone, iPad, or iPod), allowing the participant to develop awareness of typical activity and to work toward goals to improve activity levels. The mHealth platform/dashboard will allow the health coach and participant a secure space to share the data generated by the participant through the sensor, to view activity trends, and to create and track progress toward specific, measurable, attainable, relevant and time bound goals. Data elements shared to the electronic health record include: steps traveled, activities performed in minutes, calorie expenditure, and logged nutrition data. Participants can access EPIC MyChart (web page/portal) through a smartphone, tablet, or personal computer. The research team will provide individual training on the use of the technology.

3. Five bi-weekly support calls (15-30 minutes each; over 3 month intervention period): Calls will be scheduled at times chosen by the participant. The purpose of these calls is to review progress and discuss approaches to solving problems in reaching goals. On each call, the coach and participant will review the patient-generated activity data from the sensors and compare in relation to goals. They will observe and discuss trends in the data that may provide opportunities for reinforcement and highlight opportunities for continued behavior change. Following each session, the nurse coach will enter details about the current goal set by the patient, a snapshot of progress made toward goals and other relevant information into the mHealth Dashboard so that the patient, the provider and the nurse can all track and review progress.

Patient and Provider Engagement and Empowerment through Technology $(P^2E^2T^2)$ to Improve Health in Diabetes

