Patient Advisory Board Members: As part of the PCORI funding expectations, this project includes three Advisory groups: Patients, Providers and Technical/Computer Experts. The Patient Advisory Board provides input and guidance to the study team about study design, measures, recruitment strategies, and will assist in interpreting deidentified data. Several patient advisors have indicated interest in assisting with recruitment, and have offered to go to clinics to help recruit participants. Those interested will complete CITI training and will receive all appropriate training as members of the research team, and will be added to the research personnel list, before engaging in any direct contact with participants or data. We anticipate, with increased advertising of this project, we can enroll 30 participants a month. This means total enrollment would take approximately 6 months.

Significant research staff time will be devoted to conducting this research. The Project Manager has 75% time devoted to the execution, completion, and analysis of this research. Two health coaches will be hired at 75% time over a 12 month period to accommodate the extent of health coaching required during a rolling enrollment over 6 months.

25) Prior Approvals

n/a

26) Provisions to Protect the Privacy Interests of Subjects

The study staff will offer detailed explanation of the study to subjects prior to consent. It will be emphasized that all of the data collected in the study will be de-identified. All results will be analyzed in aggregate. It will be stored in a secure server and used expressly in de-identified form exclusively for the purposes of the aims of this research project.

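### Enrolment of 30 a month for about 6 months gives about 180 participants, not the target of at least 300, and Table 1's sample sizes do not follow from their labelled differences

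*Protocol*

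**What the plan says.** **Enrolment.** Protocol section 24 (Resources Available) states "we can enroll 30 participants a month. This means total enrollment would take approximately 6 months". The same section plans two health coaches at 75% time for 12 months and ties that to a 6-month rolling enrolment. Section 7 (Number of Subjects) states "According to the anticipated enrollment calculations above, we expect to enroll at least 150 patients in each of the intervention and control cohorts" and "We will not enroll more than 350 participants in total". Section 8 (Recruitment Methods), in the paragraph on advertisements, dates recruitment from January to August 2016. Section 10 states "Estimated duration of the study completion is 24 months from start of enrollment". Section 12 places the support calls "over 3 month intervention period".

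**Sample size.** Section 7 states "we expect to find self-efficacy scores to be 4.03 and 3.64, for the intervention and control group respectively, with a standard deviation of 0.70", a difference of 0.39, and then "Table 1 presents the sample size calculations for the number of eligible patients needed to detect significant differences in self-efficacy scores". Table 1 lists, at alpha 0.05 and power 0.80, 219, 134, 92, 67 and 51 per arm for differences of 0.20, 0.25, 0.30, 0.35 and 0.40. The text adds that with 100 per group the study still has at "least 80% power to detect the specified clinically important effect size". Table 1 does not state its sidedness or formula; the SAP tests its fixed effects two-sided.

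**The concern.** The enrolment rate and duration in section 24 cannot both be right if section 7's target stands. The duration is also the stated basis for the coach posts, so the resourcing is tied to an enrolment period that delivers about 120 participants fewer than planned. A reader cannot tell whether the plan is for 180, 240 or 300.

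Table 1 is the protocol's sample size calculation. Its entries differ from what its own labels and SD give, so it cannot be reproduced as printed.

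**Working it through.** **1. Enrolment** (rate and duration from section 24, target and cap from section 7, window from section 8)

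- Section 24's own product: 30 × 6 = 180. Shortfall against the target: 300 − 180 = 120.
- Section 8's window of 8 months: 30 × 8 = 240, which is 60 short.
- Time needed at 30 a month: 300/30 = 10 months; for the cap, 350/30 = 11.7 months.
- Rate needed for 300: 300/6 = 50 a month in 6 months; 300/8 = 37.5 a month in 8 months.
- Coach period, assuming steady enrolment and posts that start with enrolment: 6 + 3 = 9 months fits within 12; 10 + 3 = 13 exceeds it by about 1 month. No section gives the start of the posts.
- Study length: 10 + 9 = 19 months, which fits the 24 months.

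**2. Table 1**

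Inputs: SD 0.70 (section 7), alpha 0.05 and power 0.80 (Table 1), two-sided (SAP), equal arms. Normal formula: n per arm = 2 × [(1.960 + 0.842) × 0.70 / d]². At d = 0.20 this is 192.3, so 193. The t column uses the noncentral t distribution. The implied SD is d × √(N/2) / 2.8016.

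| Difference d | Printed N | n (z) | n (t) | Printed N × d² | Implied SD (z) | Power of printed N at d (t) |
|---|---|---|---|---|---|---|
| 0.20 | 219 | 193 | 194 | 8.76 | 0.747 | 84.7% |
| 0.25 | 134 | 124 | 125 | 8.38 | 0.730 | 83.0% |
| 0.30 | 92 | 86 | 87 | 8.28 | 0.726 | 82.4% |
| 0.35 | 67 | 63 | 64 | 8.21 | 0.723 | 81.9% |
| 0.40 | 51 | 49 | 50 | 8.16 | 0.721 | 81.5% |

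The 0.40 row is off by only 2 (z) or 1 (t). The others are off by 4 to 26 (z).

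*Could one unstated input explain the table?* With SD, alpha, sidedness and power fixed, N × d² is constant apart from rounding up. Allowing for rounding, the first row lies in (8.72, 8.76] and the last in (8.00, 8.16]. These do not overlap. Rounding up and the t correction would make N × d² rise as N falls, which is the opposite of the printed pattern. So no single SD, sidedness, power or constant inflation factor fits all five rows.

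*Are the labels shifted?* Taking 0.01 off each difference, with SD 0.70 and the normal formula:

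| d | 0.19 | 0.24 | 0.29 | 0.34 | 0.39 |
|---|---|---|---|---|---|
| n before rounding | 213.07 | 133.54 | 91.46 | 66.54 | 50.57 |
| n rounded up | 214 | 134 | 92 | 67 | 51 |
| Printed | 219 | 134 | 92 | 67 | 51 |

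Four rows match exactly, and the last is the planned difference, 4.03 − 3.64 = 0.39.

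**3. Consequence for power** (SD 0.70, two-sample t, two-sided)

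- Power for 0.39: 97.5% at 100 per arm; 96.1% at 90 per arm (180 enrolled); 92.7% at 76 per arm (90 × 0.84 = 75.6, using section 7's 16% attrition).
- Difference detectable with 80% power: 0.29 at 90 per arm and 0.32 at 76.

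**The case against.** - **The duration is only approximate.** Ten months is two thirds longer than 6, so that word does not cover the gap. Reading the rate as per arm does not rescue it either: 60 a month would give 300 in 5 months, and section 24 speaks of participants and of total enrolment.
- **The 150 per arm rests on earlier enrolment calculations.** These are not in the text available, which may be a gap in extraction. Their absence is not counted as an error, and they could not change 30 × 6.
- **A reader might infer that coaching is bound to outlast the coach posts.** The documents do not show that. The one-month overrun needs posts that start with enrolment, and no start is given. It is a point to check, not an established shortfall.
- **Table 1 may be only a labelling slip.** This is a good objection and largely stands. The 0.01 shift uses the protocol's own SD, reproduces four of five rows and ends at the planned difference. It does not produce 219, which is printed in both arm columns, so a second slip is needed. The explanation is likely, not proven.
- **Table 1 decides nothing.** This is mostly right: the 150 per arm is not attributed to any row, and every printed size is larger than its label requires.

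**Conclusion.** Both figures are wrong as written, and the matter is minor.

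1. Section 24 implies about 180 participants and section 8's window at most 240, against at least 300 in section 7. This is plain arithmetic and needs no assumption.
2. Four rows of Table 1 clearly disagree with their labels at SD 0.70, and the fifth is off by 1 to 2. The recomputed sizes assume a two-sided test, but the finding that no common input fits all five rows does not.

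A reader might infer that the trial is underpowered. The documents do not support that. Table 1 errs on the conservative side (81.5% to 84.7% power at its labels), and section 7's claim of at least 80% power for 0.39 with 100 per arm holds. Even 180 enrolled with 16% attrition would keep about 93% power for 0.39 if the stated SD is right. The issue is feasibility, resourcing and reproducibility. Nor does a 10-month enrolment break the 24-month study duration.

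**What to change.** **Enrolment.** Make the target, rate and duration agree across sections 7, 8 and 24:

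- keep 300 at 30 a month, state about 10 months and extend the January to August window to match; or
- keep the shorter period and justify the rate it needs (50 a month for 6 months, 37.5 for 8); or
- if only about 180 is attainable, restate the size in section 7 with its detectable difference at 80% power (0.29 at 90 per arm, 0.32 at 76 after 16% attrition).

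State when the coach posts start and check the 12 months against the chosen period.

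**Table 1.** Go back to the original calculation, then do one of two things:

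- relabel the differences as 0.19, 0.24, 0.29, 0.34 and 0.39 and correct 219 (214 by z), if that proves to be the cause; or
- recompute at the printed labels (193, 124, 86, 63, 49 by z; 194, 125, 87, 64, 50 by t) and add a row for the planned 0.39 (51 per arm by z), so that the planned difference is covered.

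In either case give the SD, sidedness and formula under the table.

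**Cost.** Text and table edits in sections 7, 8 and 24, and no participants beyond the existing target. If 300 at 30 a month is kept, about one further month of the coach posts might be needed, depending on their start.
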